## **PRECIS**

### **BACKGROUND**

- High dose rate brachytherapy (HDR) is a challenging technique utilized in many malignancies in order to deliver a high dose of radiation therapy to tumor in a conformal fashion with a rapid dose fall-off with the objective of sparing normal surrounding tissue
- HDR therapy has been targeted to particular subsites as an integral part of either definitive management or palliation for malignancy-related symptoms.

### **OBJECTIVES**

- The primary objective is to determine the quality of high dose rate brachytherapy implants performed in the radiation oncology branch. An implant will be adequate if 90% of the GTV receives 90% of the dose prescribed and 80% of the CTV receives 85% of the prescribed dose. An implant will be inadequate if the above dose limitations are not met.
- To evaluate local control and late toxicity rates following brachytherapy at the NCI ROB
- To increase the flow of oncology participants requiring brachytherapy to the NCI ROB, as these participants lend themselves to special study and have unique educational value for the purpose of educating nurses, medical students, residents, physicists, clinical fellows, and physicians.

### **ELIGIBILITY**

- Participants with cancer who could potentially benefit from the use of high dose rate brachytherapy as a component of their treatment.

### **DESIGN**

- Participants will undergo appropriate work-up and clinical evaluation to determine if high-dose brachytherapy would be beneficial in either primary treatment or palliation of their disease. Participants will be treated with high-dose brachytherapy appropriately sequenced with other modalities in their treatment regimen. This treatment will be administered in accordance with standard radiation oncology practice and per the ABS (American Brachytherapy Society) guidelines.
- The participant's disease status and toxicity outcomes will be documented for a 12-month period at 3 months intervals.

## **STATEMENT OF COMPLIANCE**

The trial will be carried out in accordance with International Conference on Harmonisation Good Clinical Practice (ICH GCP) and the following:

- United States (US) Code of Federal Regulations (CFR) applicable to clinical studies (45 CFR Part 46, 21 CFR Part 50, 21 CFR Part 56, 21 CFR Part 312, and/or 21 CFR Part 812)

National Institutes of Health (NIH)-funded investigators and clinical trial site staff who are responsible for the conduct, management, or oversight of NIH-funded clinical trials have completed Human Subjects Protection and ICH GCP Training.

The protocol, informed consent form(s), recruitment materials, and all participant materials will be submitted to the Institutional Review Board (IRB) for review and approval. Approval of both the protocol and the consent form must be obtained before any participant is enrolled. Any amendment to the protocol will require review and approval by the IRB before the changes are implemented to the study. In addition, all changes to the consent form will be IRB-approved; an IRB determination will be made regarding whether a new consent needs to be obtained from participants who provided consent, using a previously approved consent form.

## **1 INTRODUCTION**

### **1.1 STUDY OBJECTIVES**

#### **1.1.1 Primary**

The primary objective is to determine the quality of high dose rate brachytherapy implants performed in the radiation oncology branch. An implant will be adequate if 90% of the GTV receives 90% of the dose prescribed and 80% of the CTV receives 85% of the prescribed dose. An implant will be inadequate if the above dose limitations are not met.

#### **1.1.2 Secondary**

- To evaluate local control and late toxicity rates following brachytherapy at the NCI ROB
- To increase the flow of oncology participants requiring brachytherapy to the NCI ROB, as these participants lend themselves to special study and have unique educational value for the purpose of educating nurses, medical students, residents, physicists, clinical fellows, and physicians

### **1.2 BACKGROUND AND RATIONALE**

#### **1.2.1 High Dose Rate Brachytherapy (HDR)**

This protocol is designed to treat participants with cancer who could potentially benefit from the use of high dose rate brachytherapy as a component of their treatment. Brachytherapy, the placement of a radioactive source close to a tumor, is a well-established part of the treatment of many malignancies, both for palliative and definitive applications. High dose brachytherapy is useful in many malignancies in order to deliver a high dose of radiation therapy to tumor in a conformal fashion with a rapid dose fall-off with the objective of sparing normal surrounding tissue. Typically, high dose rate is delivered after the applicators are properly secured, dose calculations are made and a remote afterloader is activated.

Here in the department of radiation oncology, our attending physicians have experience with a Nucletron afterloader in the treatment of cervical cancer, prostate cancer and cholangiocarcinoma and seek to train our residents in these procedures as well.

#### **1.2.2 Selection of HDR Sites**

HDR is a challenging technique that can be used alone or combined with external beam therapeutic irradiation in various settings. HDR can be utilized for both definitive cases as well palliative setting for relief of obstructive symptoms or bleeding. HDR can increase the quality of life or provide a potential avenue for re-treatment in those participants already treated with external beam regimens. In this regard, HDR brachytherapy can provide a unique opportunity to study and customize therapy to each individualized participant. Common sites of disease in which the role of brachytherapy has been well described include but are not limited to gynecological tract, (endometrial or cervical cancer), pulmonary, breast and prostate cancer. HDR can be potentially useful in any clinical situation in which a high-dose of radiation is needed for tumor control while potentially sparing sensitive-surrounding critical structures.

For example, gynecologic brachytherapy has proven to be an integral treatment in curing even locally advanced malignancies while allowing sparing of the normal surrounding tissues. Gynecologic brachytherapy has proven very effective in curing even locally advanced malignancies while allowing sparing of the normal surrounding tissues. For cervical cancer, external beam radiation therapy (EBRT) and/or brachytherapy is used in the definitive management of locally advanced malignancies. In large- scale randomized trials, brachytherapy has proven useful in decreasing the risk of local recurrence for certain high-risk endometrial cancers (1). In cases of inoperable endometrial cancer, some reports have shown that this subset of participants can be treated with radiation therapy alone. Additionally, participants with potentially curable recurrences at the vaginal cuff are also possible candidates who benefit from high dose rate brachytherapy. (12)

Lung brachytherapy can be particularly helpful and may provide relatively quick relief to those who are suffering from severe local symptoms (hemoptysis, obstruction as a result of their cancer) secondary to endobronchial component or those who have received the maximum safely tolerated lung dose as a result of previous treatment with external beam radiotherapy (8).

Breast HDR brachytherapy provides a potential benefit to woman who may suffer from diminished cosmesis as a results of their larger breast size or those who are unable to travel the long distances daily for a conventional 6-week course of external radiation therapy. (6)

Prostate HDR has a long history in the radiation oncology branch in which there was significant accrual to the previous “phase II study of MR-guided high dose rate brachytherapy boosts for prostate cancer”. Guidelines from this study represent a natural extension of the protocol that we are completing here. In general, clinical evidence has shown that dose escalation in organ confined prostate cancer improves local disease control (13, 14). HDR brachytherapy represents an elegant method of accomplishing dose escalation in prostate cancer (15) but precise evidence guiding dose and fractionation is lacking (16). HDR brachytherapy has three potentially significant roles in the curative intent treatment of prostate cancer: 1) as a boost in conjunction with supplemental EBRT for intermediate and high risk prostate cancer and 2) as monotherapy in low and low intermediate risk prostate cancer and 3) as salvage for localized recurrence after prior external beam irradiation or radical prostatectomy. The use of HDR brachytherapy as a boost as per 1) has significant evidence for the ability to dose escalate by way of hypofractionation with excellent biochemical relapse-free survival rates with a low incidence of severe late genitourinary or gastrointestinal toxicities (16,17) and this has been formalized in the NCCN guidelines. The use of HDR brachytherapy as monotherapy is supported by data from several institutions (18,19) and a recent systematic review (20). Prostate-specific antigen progression-free survival using monotherapy ranged from 79% to 100% and local control from 97% to 100% with low toxicity rates. The use of HDR brachytherapy for localized recurrence while an exciting prospect remains investigational. As a whole, high dose rate brachytherapy is technically complicated but increasingly practiced in the United States with significant heterogeneity in terms of the doses and fractionations being employed. HDR for various body sites has so many advantages over low-dose rate or simple external radiation therapy which include but is not limited to: faster treatment times on an outpatient basis resulting in less resources utilized on the participant and hospital’s behalf, better optimization secondary to the ability to vary dwell time versus low-dose rate therapy and a sharp dose fall-off allowing for decreased dose to adjacent critical organs

We anticipate that the majority of participants treated will fall into one of these aforementioned subsites. However, almost all anatomic subsites have the ability to undergo HDR treatment with the objective of either primary cancer treatment or effective, expedited palliation of symptoms.

## **2 ELIGIBILITY ASSESSMENT AND ENROLLMENT**

### **2.1 ELIGIBILITY CRITERIA**

#### **2.1.1 Inclusion Criteria**

- 2.1.1.1 Pathologically confirmed malignancy for which high-dose rate brachytherapy is appropriate as a component of their therapeutic regimen.
- 2.1.1.2 Age  $\geq$  18 years of age.
- 2.1.1.3 ECOG performance status of 0, 1, or 2 (see [Appendix B](#))
- 2.1.1.4 Participant must have a primary medical or surgical oncologist in the community or at NCI who is willing to collaborate with the ROB staff in the clinical management of the participant.
- 2.1.1.5 Participants of childbearing or child- fathering potential must be willing to use a medically acceptable form of birth control, which includes abstinence, while they are being treated on this study.
- 2.1.1.6 Site-specific inclusion criteria (any one or more of the following):
  - 2.1.1.6.1 Gynecologic cancers
    - 2.1.1.6.1.1 Endometrial cancer
      - Participants at a higher risk of recurrence (because of either grade, myometrial invasion, lymphatic vascular space invasion, tumor size, lymph node status, tumor extension, presence or absence of surgical staging)
      - Participants who have suffered a recurrence at the vaginal cuff
      - Participants who are unable to undergo surgery and must have treatment for an inoperable primary endometrial cancer.
    - 2.1.1.6.1.2 Cervical cancer
      - Participants who are unable to undergo surgery and must have treatment for an inoperable primary cervical cancer.
      - Participants with locally advanced cervical cancer in whom brachytherapy will be integrated as a boost to external beam radiation either a palliative or curative setting (definitive or post-operative setting).
    - 2.1.1.6.1.3 Lung cancer
      - Participants with an endobronchial component causing symptoms
      - Participants who cannot undergo resection because of poor lung function or distant lung metastasis
    - 2.1.1.6.1.4 Breast cancer
      - Infiltrating ductal carcinoma or DCIS, stage T0, T1, and T2  $\leq$  3.0 cm, N0 and M0,

- Participants benefiting from HDR as either as a boost or accelerated partial breast irradiation regimen.

#### 2.1.1.6.4 Prostate Cancer

- Participants with localized prostate cancer (T1b-T3b) in whom brachytherapy will be integrated as a boost to external beam radiation or used as monotherapy for definitive management.

#### 2.1.2 Exclusion Criteria

2.1.2.1 Cognitively impaired participants who cannot give informed consent.

2.1.2.2 Participants receiving concurrent investigational chemotherapeutic agents.

2.1.2.3 Participants receiving concomitant chemotherapy administration in the 5 days preceding brachytherapy (except for gynecological cancer participants who may have received concurrent chemotherapy as a component of their treatment regimen)

2.1.2.4 Pregnant or breast-feeding females are excluded because of the potential mutagenic effects on a developing fetus or newborn.

2.1.2.5 Clinically significant unrelated systemic illness (serious infections or significant cardiac, pulmonary, hepatic or other organ dysfunction), which in the judgment of the Principal or Associate Investigator would compromise the participant's ability to tolerate this therapy or are likely to interfere with the study procedures or results.

2.1.2.6 Participants who are in the estimation of the PI, deemed unable or unlikely to adhere to protocol treatment.

2.1.2.7 Abnormal bleeding times or active anti-coagulation therapy.

- platelets < 100,000 per mm^3
- PT/PTT>1.5 ULN

2.1.2.8 Any participant or tumor/anatomical factors that may prevent brachytherapy apparatus from being properly and safely inserted and positioned and from radiation therapy being administered per ABS guidelines ([Appendix A](#)) (5, 6, 8, 10, 11, 12)

2.1.2.9 Participants whose malignancy has one or more of the following site-specific criteria disqualifying them from the study:

##### 2.1.2.9.1 Breast cancer:

- Participants inappropriate for standard breast conservation therapy (Multicentric disease, inability to achieve clear margins);
- male participants with breast cancer
- autoimmune disorders, including SLE, Scleroderma, etc.
- distant metastases;

##### 2.1.2.9.2 Prostate cancer:

- distant metastases
- lymph node metastases

### 2.1.3 Recruitment Strategies

This protocol may be abstracted into a plain language announcement posted on NIH websites and on NIH social media platforms.

## 2.2 SCREENING EVALUATION

Note: Screening evaluation testing/procedures are conducted under the separate screening protocol, 01-C-0129 (Eligibility Screening and Tissue Procurement for the NIH Intramural Research Program Clinical Protocols). Assessments performed at outside facilities or on another NIH protocol within the timeframes below may also be used to determine eligibility once a participant has signed the consent.

### 2.2.1 Clinical Evaluation

- All participants will have a problem-based history and directed physical examination performed. This should include measurements of disease status, stage of disease, signs, and symptoms caused by the cancer, performance status, weight and concomitant medications.
- All pertinent medical records, pathology reports, and radiographic imaging studies will be reviewed.
- Vital signs, including ECOG
- Anesthesia consult if sedation will be required

### 2.2.2 Laboratory Evaluation

- Outside Pathology report confirming histological diagnosis of cancer.
- Pre-treatment blood tests should be performed within 72 hours prior to enrollment
  - Urine Pregnancy required for females of childbearing potential
  - CBC, platelet count, PT/PTT

### 2.2.3 Radiographic Evaluation

#### 2.2.3.1 For disease sites that can be imaged, imaging of target(s) will occur within 4 weeks of enrollment.

- The appropriate imaging modality will be chosen based on the site(s) of target however if the lesion is visible on CT imaging, this will be the preferred modality for this protocol. The selected imaging modality will be used at each follow-up to determine local control.
- Additional radiographic studies will be obtained depending on the known sites of disease and as the clinical situation dictates (i.e. bone scan, plain films).
- When deemed necessary (i.e. outdated or inadequate prior studies) MRI, CT, PET scans, may be obtained to complete clinical and pathologic staging.

#### 2.2.3.2 Evaluation of target lesions

- For disease sites that can be imaged, each lesion to be treated with HDR will be clearly identified in the medical record and will be measured at baseline.
- The lesion(s) will be measured with margins defined as the largest measurement on CT, MRI, or other appropriate site-specific imaging dependent on the site of metastasis.

## **2.3 PARTICIPANT REGISTRATION AND STATUS UPDATE PROCEDURES**

Registration and status updates (e.g., when a participant is taken off protocol therapy and when a participant is taken off-study) will take place per CCR SOP ADCR-2, CCR Participant Registration & Status Updates found [here](#).

### 2.3.1 Treatment Assignment Procedures

#### **Cohorts**

Number	Name	Description
1	Gynecologic	Participants who have been diagnosed with gynecologic cancer
2	Pulmonary	Participants who have been diagnosed with pulmonary cancer
3	Breast	Participants who have been diagnosed with breast cancer
4	Prostate	Participants who have been diagnosed with prostate cancer

#### **Arms**

Number	Name	Description
1	Radiation therapy	Radiation therapy given as HDR Brachytherapy.

#### **Arm Assignment**

Participants in cohorts 1-4 will be directly assigned to arm 1.

## **3 STUDY IMPLEMENTATION**

### **3.1 STUDY DESIGN**

In this study, participants will undergo appropriate work-up and clinical evaluation to determine if high-dose brachytherapy would be beneficial in either primary treatment or palliation of their disease. Participants will be treated with high-dose brachytherapy appropriately sequenced with other modalities in their treatment regimen. This treatment will be administered in accordance with standard radiation oncology practice and per the ABS (American Brachytherapy Society) guidelines. The participant's disease status and toxicity outcomes will be documented for a 12-month period at 3-month intervals.

### **3.2 PROTOCOL THERAPY ADMINISTRATION**

#### 3.2.1 Treatment Coordination

The participant will be evaluated by study investigators as to the appropriateness and feasibility of brachytherapy on an individual basis. This will necessitate close and continued collaboration with the participant's referring oncologist. Study investigators will coordinate the timing of brachytherapy session(s) with other modalities in the participant's treatment regimen.

### 3.2.2 High Dose Rate Brachytherapy (HDR)

#### 3.2.2.1 Pre-plan

- In diseases where targets can be imaged, volumes will be outlined based on CT or ultrasound images, which include (but are not limited to) a Gross Tumor Volume (GTV), Clinical Tumor Volume (CTV), and normal structures. GTV will encompass the known tumor volume as seen clinically and on CT. CTV includes a margin for areas of suspected microscopic disease based on Clinical and imaging data. Treatment planning software will then be utilized to plan therapy in order to ensure maximum dose to the tumor while observing outlined dose constraints to the normal structures. For prostate brachytherapy, the pre-plan may be conducted prior to the brachytherapy procedure or integrated in the brachytherapy procedure as part of real-time planning.

#### 3.2.2.2 Applicator/ Catheter Placement Procedure

- If the participant is to receive sedation, instruction will be given per the anesthesia department.
- The participant will arrive in the ROB clinic the morning of the procedure and be prepared for the HDR procedure by the ROB staff.
- In diseases where catheters have been previously placed at the time of surgery (i.e., breast cancer), the participant will arrive with catheters in place. Otherwise, the participant will be positioned, the area cleansed with an antimicrobial solution and draped according to standard sterile technique. Brachytherapy applicators or catheters are inserted in anatomical sites defined by the physician and secured by sutures or packing as needed.
- If the site can be imaged, ultrasound or CT images will again be obtained.
- The placement of the applicators may be adjusted as needed based on the images until the radiation oncologists are satisfied with applicator placements.

#### 3.2.2.3 Implant Dosimetry and Treatment Planning

- In diseases where targets can be imaged, the final CT images are transferred to the treatment planning system, where optimization of dosimetry is performed. For prostate cancer, planning is accomplished based on ultrasound imaging to which other imaging modalities may be fused.

#### 3.2.2.4 Radiation Delivery

- Participants will be transferred to the NRC approved brachytherapy treatment room in the ROB. A radiographic film may be obtained on the treatment table and applicators may require a final adjustment at that time.
- Once a treatment plan has been completed, verified and accepted, the brachytherapy will be administered with a remote afterloading system using a stepping Ir source. (Nucletron Inc.)
- Radiation delivery will take approximately 10-30 minutes depending on the strength of the source and the dose to be delivered.
- Suggested guidelines for proposed radiation doses are included in the [Appendix A](#).

#### 3.2.2.5 Device Removal

- HDR applicator/ catheters will be removed by ROB investigators or the appropriate clinical staff.

### **3.3 TREATMENT MODIFICATIONS**

Modifications to the radiation treatment plan will be made at the discretion of the radiation oncologist. Deviations from the planned treatment schedule may be required secondary to expected toxicity.

### **3.4 ON STUDY EVALUATION**

#### **3.4.1 Active Treatment Phase**

- Pre-plan obtained ([3.2.2.1](#))
- Applicator/ Catheter Placement Procedure ([3.2.2.2](#))
- Implant Dosimetry and Treatment Planning ([3.2.2.3](#))
- Radiation Delivery ([3.2.2.4](#))
- Device removal ([3.2.2.5](#))

#### **3.4.2 Post-Active Treatment Phase**

- Following completion of protocol therapy, participants will be seen in follow-up. Follow-up evaluations should occur at NIH at one month after the completion of radiation therapy, at three months after completion of radiation therapy, followed by every 3 month intervals up to 12 months
- Follow- up evaluations will include:
  - Clinical Evaluation- complete interval history and directed physical examination, notation of any ongoing or recently delivered systemic therapy
  - Any medical procedures/tests will be based on the participant's diagnosis, treatment, and supporting clinical information.
  - Assessment of acute and long-term effects of radiation therapy using the RTOG and CTC 4.0
  - In diseases where targets can be imaged, CT, MRI, or other appropriate imaging of the tumor site(s). In general, CT will be the preferred imaging modality unless the lesion is not visible on this modality. PSA will be adequate for follow up in prostate participants unless otherwise indicated.
  - Scoring of local control at each treated site will be based on RECIST criteria (limited to local disease status). Each site will be scored separately.

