## 5 DATA COLLECTION AND EVALUATION

### 5.1 DATA COLLECTION

The PI will be responsible for overseeing entry of data into an in-house password protected electronic system (C3D) and ensuring data accuracy, consistency and timeliness. The principal investigator, associate investigators/research nurses and/or a contracted data manager will assist with the data management efforts. All data obtained during the conduct of the protocol will be kept in secure network drives or in approved alternative sites that comply with NIH security standards. Primary and final analyzed data will have identifiers so that research data can be attributed to an individual human subject participant.

- Clinical data and acquired images will be recorded in a NCI CCR database (C3D).
- Clinical data collection will include: demographic information, pathologic diagnosis, clinical stage, history including prior and concurrent therapies, location and measurement of lesions, CT reports, lab reports, vital signs, dose of radiation delivered, and toxicity assessment.
- The results of any procedures and/or tests will be included in the participants' hospital chart and/or research records as appropriate. Data from these records may be used in research and scientific publications.
- Data collected may be used anonymously, for publications not originally specified, concerning the disease processes and long term effects of treatment. The data may also be used as the basis for new protocols.

All AEs, including clinically significant abnormal findings on laboratory evaluations, regardless of severity, will be followed until return to baseline or stabilization. Document AEs from the first study intervention through 30 days after the intervention was last administered. Beyond the 30 days after the last intervention, only adverse events which are serious and related to the study intervention need to be recorded.

An abnormal laboratory value will be considered an AE if the laboratory abnormality is characterized by any of the following:

- Results in discontinuation from the study
- Is associated with clinical signs or symptoms
- Requires treatment or any other therapeutic intervention
- Is associated with death or another serious adverse event, including hospitalization.
- Is judged by the Investigator to be of significant clinical impact

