### **5.3 TOXICITY CRITERIA**

The study will use the RTOG/EORTC Radiation Morbidity Scoring Scheme to score late effects of radiation treatment. The RTOG scoring criteria can be obtained from the RTOG website:

- Acute:  
<https://www.rtog.org/ResearchAssociates/AdverseEventReporting/AcuteRadiationMorbidityScoringCriteria.aspx>, and
- Late:  
<https://www.rtog.org/ResearchAssociates/AdverseEventReporting/RTOGEORTCLateRadiationMorbidityScoringSchema.aspx>

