Evaluating local control and late toxicity rates following brachytherapy are also objectives of this study. Other studies at NCI and at other institutions have found acceptable toxicity rates (16, 22, 23, 24). We will tabulate local control and late toxicity rates by stratum and combined over all four strata.

The maximum accrual will be 28 participants to each of the 4 strata (maximum accrual of 112 participants). We anticipate that accrual will be completed in 5 years.

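### With no graded baseline before HDR, late toxicity cannot be reliably separated from radiation morbidity already present

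*Combined protocol and SAP*

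**What the plan says.** Section 1.1.2 makes late toxicity after brachytherapy a secondary objective. Section 7 gives its whole analysis in one sentence: "We will tabulate local control and late toxicity rates by stratum and combined over all four strata".

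The measurement is set out in Section 3.4.2, among the evaluations at one month, three months and then every three months to month 12: "Assessment of acute and long-term effects of radiation therapy using the RTOG and CTC 4.0". Section 5.3 names the RTOG/EORTC scheme as the scale "to score late effects of radiation treatment". The active-treatment list in Section 3.4.1 contains no toxicity grading.

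Before treatment, Section 2.2.1 asks for a history and examination: "This should include measurements of disease status, stage of disease, signs, and symptoms caused by the cancer, performance status, weight and concomitant medications". No RTOG or CTC grade is requested, nor are residual effects of earlier radiation. Section 5.1 collects "history including prior and concurrent therapies", and starts adverse event recording at the first study intervention.

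On the population, Section 1.2.2 says HDR can "provide a potential avenue for re-treatment in those participants already treated with external beam regimens", and names for lung brachytherapy "those who have received the maximum safely tolerated lung dose as a result of previous treatment with external beam radiotherapy". The same background section lists salvage after external beam among the roles of prostate HDR, and Appendix A (part E) gives a salvage regimen. Section 3.6 and Appendix A also allow external beam in the same course. For cervical cancer, implants may come during or after it. No criterion in Section 2.1 limits prior radiation.

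**The concern.** A rate of late toxicity following brachytherapy is meant to describe what arises after the implant. Someone who arrives with a graded late effect of earlier external beam, or with effects of external beam given just before HDR, can carry that grade into the follow-up visits. Because the scored item is an effect of radiation therapy in general, such a persisting effect meets the wording. Nothing in Section 7 tells the analyst to leave it out.

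At stake is the interpretation of one secondary result. Prior exposure plausibly differs between the gynecologic, pulmonary, breast and prostate strata. Differences between stratum rates could then partly reflect who was enrolled, and the combined rate would depend on the case mix. A baseline grade that was never recorded cannot be reliably rebuilt afterwards from an ungraded history.

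**Working it through.** **1. The plan's own figures.** The documents give no expected late toxicity rate, precision target or sample size for this objective, so there is no stated figure to reproduce. The relevant denominator comes from the primary design: 9 participants in stage 1, 19 more if at least 7 implants are acceptable, and success at 23 or more of 28. An exact two-stage binomial calculation gives a false-acceptance probability of 0.0340 at 65% (plan: below 0.04) and power of 0.9103 at 90% (plan: above 0.90). The 28 per stratum and 112 in total therefore stand. They rest on dosimetry alone, which morbidity scoring does not touch.

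**2. Is there any graded pre-treatment record?**
- Screening (2.2.1): ungraded, and directed at cancer signs and symptoms.
- Active phase (3.4.1): no grading listed.
- Adverse events (5.1): recorded from the first intervention, so none before it. The section follows events until they return to baseline, but nothing requires that baseline to be scored.
- Clinical data list (5.1): includes toxicity assessment without a time, so a grade at entry is possible but not required.
- By contrast, for local control Section 2.2.3.2 does require a baseline measurement of each imageable lesion.

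**3. Is there an attribution rule for the table?** Attribution appears in two places: grade 4 toxicity leading to removal (3.8.2.2) and adverse events beyond 30 days (5.1). Neither is linked to the tabulation in Section 7.

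**4. Size, by assumption only.** Let *b* be the share entering with a graded effect that persists, and *t* the share developing a new late effect, independent of *b*. If every persisting effect is counted and none is attributed elsewhere:

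tabulated rate = 1 − (1 − *b*)(1 − *t*)

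With *t* = 5%:

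| *b* | Calculation | Tabulated rate | Participants of 28 |
|---|---|---|---|
| 0% | 1 − 1.00 × 0.95 | 5.0% | 1.4 |
| 10% | 1 − 0.90 × 0.95 | 14.5% | 4.1 |
| 20% | 1 − 0.80 × 0.95 | 24.0% | 6.7 |
| 30% | 1 − 0.70 × 0.95 | 33.5% | 9.4 |

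With *t* = 10%, the rates for the same values of *b* are 10%, 19%, 28% and 37% (2.8, 5.3, 7.8 and 10.4 of 28). A stratum that stops after stage 1 has 9 participants. The rates are unchanged, but the expected counts at *t* = 5% are 9 × 0.05 = 0.45, 9 × 0.145 = 1.3, 9 × 0.24 = 2.2 and 9 × 0.335 = 3.0.

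**5. Direction.** The formula can only raise the rate. Section 7 does not, however, name the data source. If the table were built from adverse event records, Section 5.1 requires only serious and treatment-related events beyond 30 days. That limit would lower the late toxicity rate.

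**The case against.** The strongest reply is that clinicians attribute before they score. The scales ask for effects of radiation, the history and records are reviewed, prior therapies are captured, and cancer symptoms are noted at entry. An assessor could set aside what was there before. The table is also descriptive, with no threshold or test attached.

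Much of this stands, and it rules out several stronger readings that a reader might infer:
- *That the rates will contain carried-over morbidity.* This is an inference. Case-by-case attribution is possible, though the plan neither requires nor describes it.
- *That the distortion is mostly upward.* The adverse event limit after 30 days could act the other way, depending on the source used.
- *That symptoms of the disease are counted too.* Airway obstruction or poor lung function from cancer is not a radiation effect, and cancer symptoms are recorded at baseline. The ambiguity concerns radiation effects.
- *That a comparison with published toxicity rates is spoiled.* Section 7 mentions such rates but plans no formal comparison.
- *That every stratum is heavily pre-irradiated.* The re-treatment statements are background, not eligibility. The prostate inclusion criterion (2.1.1.6.4) names boost and definitive monotherapy only, while salvage appears in Section 1.2.2 and Appendix A. Those passages must be reconciled.

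The reply does not remove the gap itself. Attribution to radiation in general does not separate HDR from earlier external beam, and an ungraded history does not show whether an effect has worsened.

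**Conclusion.** The point holds in this form: as written, late effects arising after HDR cannot be reliably separated from radiation morbidity present at the first HDR fraction, so the tabulated rates may be inflated to a degree that differs by stratum. The case is clearest for lung and prostate salvage, and for participants given external beam before HDR in the same course.

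The size is not computable from the documents. The range of 5% to 33.5% rests on an assumed 0% to 30% baseline prevalence, a 5% new-event rate, independence, full persistence and no attribution. With no baseline morbidity there is no inflation. The issue is confined to a descriptive secondary objective and leaves the primary conclusion untouched. It should still be corrected, because the missing information cannot be reliably recovered later and is cheap to collect.

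**What to change.** 1. In Section 2.2.1 or 3.4.1, require one RTOG late-morbidity and CTC 4.0 score at the clinical examination before the first HDR fraction. Where external beam falls between screening and HDR, take the score after it, for example when the participant is prepared for the first procedure.
2. In Section 7, state that late toxicity is taken from the scheduled RTOG/CTC scores, not from adverse event records, and counts effects that are new or at least one grade worse than the pre-HDR score.
3. Show the rates descriptively by prior or concurrent external beam, using the therapy history that Section 5.1 already collects.

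The cost is one added scoring form and a sentence or two in Section 7. Because screening runs under a separate protocol and may use outside assessments, the form must be tied to this protocol's own pre-HDR examination. The split will have small cells, since a stratum has at most 28 participants, so it should stay descriptive. A baseline score removes morbidity already present. It cannot separate HDR effects from late effects of same-course external beam that emerge afterwards, which is why the split is also needed.
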